#### 2.6.2 Secondary clinical outcomes

The following outcomes will be measured at 3, 6 and 12 months post-randomisation.

1. HRQoL: PROMIS® 29+2 Profile v2.1 (PROPr) at 6 and 12 months post randomisation. This form includes all 29 items from PROMIS® 29 Profile v2.1, plus two Cognitive Function abilities items. The 29 items from PROMIS® 29 Profile v2.1 are from the following forms;

Items	Number of items
PROMIS SF v2.0 Physical Function	4
PROMIS SF v1.0 Anxiety	4
PROMIS SF v1.0 Depression	4
PROMIS SF v1.0 Fatigue	4
PROMIS SF v1.0 Sleep Disturbance	4
PROMIS SF v1.0 Ability to Participate in Social Roles and Activities	4
PROMIS SF v1.0 Pain Interference	4
Cognitive Function SF v2.0	2
PROMIS SF Pain Intensity	1

A single overall preference score ranging from -0.2 to 1 (perfect or ideal health) is generated using sub-scores from the multiple forms. Zero indicates as state equal to death and a negative value indicates worse than death. This outcome will be scored anonymously using the HealthMeasures Scoring Service

(https://www.assessmentcenter.net/ac\_scoringservice), as recommended by the PROMIS Adult Profile Scoring Manual.

2. Dyspnoea: PROMIS dyspnoea severity Short Form. Exertional dyspnoea is a commonly reported symptom in COVID-19 survivors, thus specific questions have been added [9]. The dyspnoea short form includes 10 questions, with each response ranging from 0 to 3, giving a total raw score ranging from 0 to 30 (higher scores indicate worse severity). This measure will be scored using the HealthMeasures Scoring Service (https://www.assessmentcenter.net/ac\_scoringservice).

3. Cognitive function: Neuro-QoL Short Form v2.0 - Cognitive Function [13]. Given the high incidence of cognitive impairment in COVID-19 survivors we have added additional PROMIS questions, to obtain a measure of cognitive function. The Cognitive function short form has 8 items, with total raw scores ranging from 8 to 40 (higher scores indicate better cognitive function). This measure will be scored using the HealthMeasures Scoring Service (https://www.assessmentcenter.net/ac\_scoringservice).

4. Health utility: Euroqol EQ-5D-5L [10]. Validated, generic HRQoL measure consisting of five dimensions, each with five levels. Each combination of answers can be converted into a health utility score. It has good test-retest reliability, is simple to use, and gives a single preference-based index value for health status that can be used for cost-effectiveness analysis. A statement by NICE highlighted serious concerns regarding the EQ-5D-5L tariffs published by Devlin et al [11]. For that reason, the crosswalk value set will be used to map from the EQ-5D-5L to EQ-5D-3L using previously used and more reliable tariff values. The EQ-5D score ranges from <0-1 where a higher score reflects better quality of life.

5. International Physical Activity Questionnaire (IPAQ short-form). The IPAQ is a wellestablished activity measure reported as metabolic equivalent task (MET)-minutes per week derived from duration of walking, moderate and vigorous exercise [12] The questionnaire will be scored using the IPAQ Scoring protocol

(https://sites.google.com/site/theipaq/scoring-protocol).

6. PTSD symptom severity: The Impacts of Events Scale-Revised (IES-R) a 22 item selfreport measure of difficulties people sometimes face after stressful life events. It has been widely used in studies of survivors of ICU admission, including COVID admissions. It is part of recommended outcomes for studies of respiratory failure survivors [13-15]. The IES-R is scored by summing the response to each of the 22 questions, which each range from 0 (not at all) to 4 (extremely), making a total score range of 0-88. A score of  $\geq$ 11 on the IES-6, an abbreviated version extracted from the longer 22-item IES-R, will be taken to be indicative of case level disorder.

7. Depressive and anxiety symptoms: Hospital Anxiety and Depression Scale (HADS). A 14-item questionnaire from which anxiety and depression subscales can be derived. 7 item sub-score values ≥11 points identify case-level anxiety/depression. The HADs is widely used and a well validated measure in clinical populations [16]. The scores are simply summated to give an anxiety and depression score both ranging from 0-21 where a higher score reflects more severe symptoms of anxiety and depression.

8. Death measured using GP record. Data will be requested from general practices on completion of the trial.

#### Timing and format of data collection

Patient reported outcomes are collected online at baseline pre-randomisation, and at three months, six months and 12 months post-randomisation. Participants receive an email notification and/or text message to remind them to complete the online questionnaires at each follow-up time point. In the case of non-response to text messages, participants are contacted by telephone for collection of two core outcomes: the PROPr (primary outcome) and EQ-5D-5L.

Fluency in English is not an inclusion criterion for this study. For those not fluent in English, we will aim to collect all outcomes (or as many as possible) verbally at each follow-up. As a minimum, a core data outcome set including the PROMIS® 29+2 Profile v2.1 (PROPr) and EQ-5D-5L questionnaires will be collected orally by a bilingual researcher, where necessary, to ensure that those not fluent in English are able to contribute participant reported outcomes to the study. The EQ-5D-5L is well validated for verbal administration.

Long-term follow-up beyond 12 months: Consent will be sought from participants to hold their personal data, and at the end of the 12-month follow-up period, to request a copy of the participant's medical record from their GP. This will only be requested if the participant has not responded to the 12-month follow-up or if we know the participant has died. This will provide information on GP consultations and include copies of any hospital discharge letters allowing us to accurately cost in-patient care costs. Where appropriate, we will triangulate data from GP records and any participant self-report to achieve a robust estimate of health service activity and mortality.

#### 2.6.3 *Symptoms sub-study*

Study sites identifying patients will record information on patient hospital admission data including length of hospital stay and ventilation type. This will be pseudonymised using a screening ID number assigned to each patient by the study site. Any patients approached by a study site will provide their screening ID number and using this screening ID number, for those patients consenting to the study, WCTU will request pseudonymised data for that individual from the study site that approached the participant. Ongoing COVID-19 symptoms will be collected during the initial online eligibility assessment, supplemented by the external clinical expertise from the TSC and DMC. This will allow us to compare selected factors including patient characteristics and COVID-19 admission characteristics, and ongoing COVID-19 symptoms profile of those who take part in the study. Where possible, this sub-study will be undertaken.

#### 2.7 Hypothesis framework

For each of the primary and secondary outcomes, the null hypothesis will be that there is no true difference in treatment effect between the intervention arms.

#### 2.8 Sample size

We had no data on which to base a sample size estimation for the study. There are no normative data for the PROPr quality of life scores in this Covid-19 population and no external indication of what might be a worthwhile benefit from the intervention on quality of life outcomes for this population. American values for the general population in the USA are a mean score of 50 (1-100 scale) with an SD of 10. Whilst not our preferred practice, we have used the approach of looking for a small to moderate standardised mean effect size of 0.3. Allowing for a clustering effect in the intervention arm, we assume that a group size will consist of a maximum of eight participants. Then assuming an intra cluster coefficient (ICC) of 0.01, 90% power and type I error rate of 5%, with a 10% loss to follow-up, we require 535 participants. This equates to 272 participants in the intervention arm across up to 34 intervention groups and 263 participants in the control arm (control:intervention = 1:1.03), using computations recommended by Moerbeek [17].

The sample size was revised as requested by the data monitoring committee (DMC) in the DMC meeting (14 January 2022). However, following this meeting because of the change in recruitment strategy and thus the large recruitment from the NHS Digital mass mailouts there was no need to update the sample size. The recruitment of the trial was completed in few months following the meeting and finally 585 participants were recruited. We overrecruited to compensate the higher lost to follow-up (15%) in the observed data.

#### 2.9 Randomisation

Randomisation is undertaken automatically by the WCTU system following completion of the baseline questionnaire using a computer-generated randomisation sequence, performed by minimisation and stratified by:

- 1. age (i. <65; ii. ≥65 years),
- 2. level of hospital care (i. ICU/HDU; ii. ward),

3. case level mental health disorder (i. IES-6 PTSD score  $\geq 11/24$  or HADS Anxiety subscore  $\geq 11/21$  or HADS Depression sub-score  $\geq 11/21$ ; ii. IES-6 PTSD score < 11/24 and HADS Anxiety sub- score < 11/21 and HADS Depression sub- score < 11/21).

Participants are randomised strictly sequentially at study level.

#### 2.10 Data collection schedule

All data are entered directly by participants, UHCW staff, REGAIN practitioners or WCTU study team members onto a secure online study database hosted by WCTU as outlined in the data management plan and in accordance with the Warwick SOPs. Data entered onto the online study database are considered source data. This will be stored safely and securely. On all study-specific documents, other than the completed consent form, the participant will be referred to by the study participant number, not by name. Various methods will be used to chase missing data including phone, text and email. The procedures for managing this will be outlined in the data management plan and appropriate consent will be sought to contact participants. Data will still be collected for participants who discontinue or deviate from the intervention protocol, unless they withdraw their consent.

	Pre-randomisation			Post-randomisation			
Online assessment	1	2	3	4	5	6	
Assessment time point	Screening	Enrolment (Baseline)	Intervention Delivery 0- 8 weeks (+/- 2 weeks)	3m (± 2w)	6 m (± 1 m)	12 m (± 1 m)	
Invitation letter and flyer posted	✓						
Initial Eligibility Assessed	~						
Concomitant Illnesses		~					
Eligibility check* (telephone)		~					
Informed consent		~					

#### Table 1: Study assessments and data collected at Trial time points

	Pre-randon	nisation Post-randomisation				
Online assessment	1	2	3	4	5	6
Assessment time point	Screening	Enrolment (Baseline)	Intervention Delivery 0- 8 weeks (+/- 2 weeks)	3m (± 2w)	6 m (± 1 m)	12 m (± 1 m)
Patient Demographics		✓				
PROMIS ® 29+2 Profile v2.1 (PROPr)		✓		✓ 	✓	✓
PROMIS dyspnoea		✓		~	~	√
PROMIS Neuro- QoL		✓		~	~	√
EQ-5D-5L		✓		✓	✓	✓
IPAQ-SF		✓		✓	✓	✓
IES-R		✓		✓	✓	✓
HADS		$\checkmark$		✓	✓	✓
Intervention			$\checkmark$			
Adverse events			$\checkmark$			
Overall health		$\checkmark$		✓	✓	✓
Death						$\checkmark$

\* Eligibility check will be performed in person over the telephone by clinical member of the research team at UHCW. All other assessments and information will be completed by the participant online.

For long term follow-up assessments, consent will be sought from participants to keep their personal data. Consent will also be taken to request a copy of the participant's medical record from their GP, should they not respond to the 12-month follow-up questionnaire, or have died at the end of the study follow-up period. This will provide information on GP consultations and include copies of any hospital discharge letters allowing us to accurately cost in-patient care costs. Mortality data will be gathered from GP records at 12 months.

#### 2.11 Data monitoring and interim analysis

All study data will be supplied in strict confidence to the independent DMC for independent assessment and evaluation. The DMC will consist of independent experts with relevant clinical research, and statistical experience. The DMC meeting frequency will be guided by the DMC chair but will be suggested to be six months into the recruitment phase and regularly thereafter, as directed by the DMC chair. Confidential reports containing recruitment, protocol compliance, safety data and informal interim assessments of outcomes will be

reviewed by the DMC. The DMC will advise the TSC as to whether there is evidence or reason why the trial should be amended or terminated. The membership of the DMC has been approved and appointed by the NIHR.

There are no formal interim analyses for this study.

#### 2.12 Trial reporting

The trial will be reported in line with the CONSORT (Consolidated Standards of Reporting *T*rials) statement[18].

#### 3 ANALYSIS

#### 3.1 Subject population

#### 3.1.1 Intention-to-treat

The primary analysis and any secondary analyses will be applied to an all-randomised population on an intention-to-treat (ITT) basis. That is, any subject randomised into the trial, regardless of whether they received trial intervention and regardless of protocol deviations, unless specified.

#### 3.1.2 Missing data

Whilst every effort will be made to ensure complete data collection, it is inevitable that some data may not be available due to voluntary withdrawal of participants, lack of completion of individual data items or general loss to follow-up. Where possible the reasons for data 'missingness' will be ascertained and reported. The nature and pattern of the missingness will be carefully considered, including whether data can be treated as missing completely at random. If judged appropriate, missing data will be imputed using the multiple imputation facilities available in statistical analysis software.

If imputation is undertaken, the resulting imputed datasets will be analysed, together with appropriate sensitivity analyses. Any imputation methods used for scores and other derived variable will be carefully considered and justified. Reasons for ineligibility, non-compliance, withdrawal, or other protocol violations will be stated, and any patterns summarised. If the missing data is considered missing at random or missing completely at random, we will use imputation techniques, such as Multiple Imputation by Chained Equations (MICE), to impute missing data. The number of imputed datasets will be determined by the proportion of missing data. Usually 10-20 datasets would be sufficient for 10-30% missing data [19].

More formal analysis, for example using logistic regression with 'protocol violation' as a response, may also be appropriate and aid interpretation.

#### 4 DESCRIPTIVE ANALYSES

#### 4.1 Participant throughput

Screening data will be checked to identify any characteristic differences between those individuals in the trial, those ineligibles, and those eligible but withholding consent. A CONSORT chart illustrating participant flow throughout the trial will also be produced which will describe the following: number of participants randomised, allocated to each intervention, delivered and not delivered intervention, lost to follow-up, and included in ITT analysis population at different time points.

#### 4.2 Baseline comparability of randomised groups

Baseline data will be summarised to check comparability between treatment arms. The number and percentage will be presented for categorical variables. The mean and standard deviation or the median and the interquartile range (IQR) will be presented for continuous variables, or the range if appropriate. There will be no tests of statistical significance performed nor confidence intervals calculated for differences between randomised groups on any baseline variable.

#### 4.3 Losses to follow-up

The number and percentage of participants lost to follow-up before 12 months postrandomisation will be reported for each randomised group.

#### 4.4 Adherence to treatment

The number and proportion of patients who did and did not receive the intervention they were allocated to will be reported. Full compliance with the online, exercise and psychological REGAIN intervention will be defined as attending the initial assessment, plus attending four out of six psychological support sessions, AND five out of eight live exercise sessions.

#### 5 COMPARATIVE ANALYSES

All analyses will be conducted as ITT unless otherwise specified.

The screening data collects; Date of admission, Date of discharge and ventilation support (highest level of ventilation support during admission: Invasive ventilation [highest level]/Non-invasive ventilation/CPAP [lowest level]). A CONSORT chart illustrating participant flow throughout the trial will also be produced. Standard statistical summaries will be presented for the primary outcome measure and all secondary outcome measures.

For continuous outcomes, mean treatment difference with 95% confidence interval (CI) will be reported. For categorical outcomes, odds ratio with 95% CI will be reported. Plots will also be produced for the primary outcome and some of the secondary outcomes to check the comparability between treatment arms.

#### 5.1 Primary analysis

#### 5.1.1 *Primary outcome*

The main analyses will be for overall treatment effect. The primary analysis will use a linear regression (heteroscedastic) model to estimate the treatment effects (95% confidence intervals (CI)), adjusted for baseline as well as adjusted for stratification variables, important patient-level covariates and group effect. The reason for using heteroscedastic model is the variance is different between the arms as the control arm is non-clustered and the intervention arm is clustered [20]. In the trial, the control arm receives individual therapy whereas the intervention arm receives group therapies. The groups or therapist effect will be treated here as random effects. If there is negligible group and centre effect, then the usual linear regression will be used for the analysis.

The main analysis will be carried out on the stratification variables such as:

- Age (continuous)
- Level of hospital care (i. ICU/HDU; ii. ward)
- Case level mental health disorder (i. IES-6 PTSD score ≥11/24 or HADS Anxiety subscore ≥11/21 or HADS Depression sub-score ≥11/21; ii. IES-6 PTSD score <11/24 and HADS Anxiety sub- score <11/21 and HADS Depression sub- score <11/21)

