6.2 Statistical analysis of efficacy and harms

6.2.1 Statistics and data analysis

A detailed statistical analysis plan will be written and approved by the Data Monitoring Committee (DMC).

Data will be summarised and reported as per CONSORT, using intention-to-treat analyses.

For the primary outcome measures, treatment effects (with 95% Confidence Intervals) will be estimated using hierarchical linear regression models, Both unadjusted and adjusted (for stratification variables and important patient-level covariates) will be presented. We will estimate and adjust for site effects as a random variable in the model. Other secondary outcomes which are

continuous will be analysed in a similar way. Secondary outcomes which are categorical will be analysed using logistic regression models. We will assess compliance using Compliers Average Causal Effect (CACE) analysis. In the case of missing outcome data, we will compute sensitivity analyses using imputation techniques to examine the impact of missingness.

There are no formal interim analyses for this study.

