#### 5.2 Secondary analyses

For the primary outcome, we will also use a linear regression (heteroscedastic) to estimate the treatment effect, without adjustment of any covariates but adjusting the therapist random effects.

All secondary continuous outcomes (including the health economic outcomes, EQ-5D-5L index and VAS scores) will be analysed using the linear regression (heteroscedastic) specified in the primary analysis method, with the same adjustment. An unadjusted analysis will also be conducted for each outcome.

We will assess the impact of compliance on outcomes using a CACE (Compliers average causal effect) analysis for the primary outcome. CACE models evaluate the average effect of the intervention in participants who comply with their allocated treatment. This preserves randomisation groups and eliminates introducing any potential confounders introduced by PP analysis.

For categorical outcomes, odds ratio with 95% CI will be reported. We will also plot the data over time, with the mean and confidence intervals, for some of the secondary outcomes such as the International Physical Activity Questionnaire (IPAQ short-form).

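### The SAP lets the primary model drop its clustering term on an undefined, data-based criterion and does not settle the clustering unit; the likely effect on error is small and the fix is nearly free

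*SAP*

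**What the plan says.** SAP 5.1.1 specifies a linear heteroscedastic model for the primary outcome, adjusted for baseline, the stratification variables, other patient covariates and a group effect. Its stated reason is a design fact: one arm is clustered and the other is not. On the unit it says "The groups or therapist effect will be treated here as random effects". It then gives the exception: "If there is negligible group and centre effect, then the usual linear regression will be used for the analysis". Centre is not among the effects that the section puts in the model.

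Other sections name the clustering differently:

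- SAP 5.2, unadjusted analysis of the primary outcome: "without adjustment of any covariates but adjusting the therapist random effects".
- SAP 5.2, secondary continuous outcomes: the primary method, so the same open choice carries over.
- SAP 5.3, subgroups: a hierarchical linear model with no level named.
- Protocol 6.2.1: "We will estimate and adjust for site effects as a random variable in the model". It has no fallback.
- SAP 2.8 (and Protocol 6.1), sample size: "Allowing for a clustering effect in the intervention arm, we assume that a group size will consist of a maximum of eight participants", with 272 intervention participants in up to 34 groups.

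SAP 2.5.1 says that participants stay in one group for the eight weeks. SAP section 8 declares no deviation from the protocol analysis.

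**The concern.** Two things are left open in the one analysis that should have none.

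The first is the switch. The clustering comes from how the treatment is delivered, and a small estimated variance does not remove it. With about 34 groups of seven or eight, the between-group variance is poorly estimated, so a low or non-significant value is common even when real clustering exists. Dropping the term in those trials means using the smaller standard error when the data happen to understate the clustering.

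The second is the unit. Group, therapist and site imply different covariance structures and so can give different standard errors. As written, the adjusted and unadjusted analyses of the primary outcome may differ in clustering unit as well as in covariates.

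At stake are full prespecification of the primary confidence interval and a possible small excess of false positives.

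**Working it through.** **Inputs (SAP 2.8 and 5.5).** "small to moderate standardised mean effect size of 0.3"; "a group size will consist of a maximum of eight participants"; "assuming an intra cluster coefficient (ICC) of 0.01, 90% power and type I error rate of 5%, with a 10% loss to follow-up"; two-sided tests; 272 intervention and 263 control.

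**1. Reproduce the sample size, to see which unit it assumes.** Take SD = 1 and clustering in the intervention arm only.

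- Design effect = 1 + (8 − 1) × 0.01 = 1.07.
- Optimal allocation = √1.07 = 1.034, matching the stated 1.03.
- Control = (1.960 + 1.282)² / 0.3² × (1 + 1.07/1.034) = 237.5. Intervention = 237.5 × 1.034 = 245.7.
- Divide by 0.9: 263.9 + 273.0 = 536.9, against 535 stated.
- Without clustering: 468 evaluable, 520 after loss.

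So 535 reproduces with therapy group as the cluster.

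**2. Ordinary regression that always ignores groups.** Evaluable: 272 × 0.9 = 244.8 and 263 × 0.9 = 236.7. True SE = √(DE/244.8 + 1/236.7); naive SE = √(1/244.8 + 1/236.7) = 0.0912. Type I error = 2 × [1 − Φ(1.96 × naive/true)]. Group size 8; ICCs above 0.01 are assumptions.

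| ICC | DE | True SE | True/naive | Type I error |
|---|---|---|---|---|
| 0.01 | 1.07 | 0.0927 | 1.017 | 5.4% |
| 0.03 | 1.21 | 0.0957 | 1.050 | 6.2% |
| 0.05 | 1.35 | 0.0987 | 1.083 | 7.0% |
| 0.10 | 1.70 | 0.1057 | 1.159 | 9.1% |

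**3. The two-step procedure.** The SAP does not define *negligible*, so two triggers were assumed: a between-group F-test with p > 0.05, and an estimated ICC below 0.01. The simulation used 200,000 null trials per ICC, 34 groups of 7, 237 controls and no covariates, with a Satterthwaite t-test when the term is kept.

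| True ICC | Dropped, F-test | Type I error, F-test | Dropped, ICC < 0.01 | Type I error, ICC < 0.01 | Type I error, always kept |
|---|---|---|---|---|---|
| 0.01 | 91% | 5.1% | 53% | 4.6% | 5.0% |
| 0.03 | 80% | 5.6% | 34% | 4.9% | 5.0% |
| 0.05 | 66% | 5.7% | 20% | 4.9% | 5.0% |
| 0.10 | 28% | 5.4% | 4% | 5.0% | 5.0% |

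Runs with 250 controls agree: about 5.0 to 5.2% at ICC 0.01 with the F-test trigger. A third assumed trigger, estimated ICC below 0.05, drops the term in 84% of trials at ICC 0.01 and gives 5.0 to 5.4% over ICC 0.01 to 0.10.

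**4. Power if the term is always kept (ICC 0.01).** Power = Φ(0.3/√(1.07/n_I + 1/n_C) − 1.96).

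- 535 with 10% loss: n_I = 244.8, n_C = 236.7, giving 89.9%.
- 585 with the 15% loss reported in SAP 2.8, split 1.03:1: n_I = 252.3, n_C = 245.0, giving 90.8%.

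**The case against.** The best case against is that this does almost no harm. At the only ICC in the documents, 0.01, the two-step procedure has essentially nominal error under every trigger tried. The larger values need ICCs that the documents do not give. At ICC 0.01 ignoring groups understates the SE by a factor of 1.017, so a p-value of 0.050 becomes about 0.054, which matters only for a borderline result. The share of trials in which the term is dropped also overstates how often results differ: at ICC 0.01 with 34 groups of 7, the between-group mean square falls below the within-group one in about 42% of trials, and a mixed model with a non-negative variance would then set the group effect to zero anyway. Finally, the intended unit can be recovered, since the SAP adjusts for group and sizes the trial on it.

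All of this stands as to size. It does not supply a criterion, nor reconcile group, therapist and site.

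A reader might infer more than the documents support:

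- **Larger inflation through therapist clustering.** This requires therapists to be nested in the intervention arm. Protocol 1.5 and SAP 2.5.1 have REGAIN practitioners seeing both arms, so therapist is at least partly crossed with arm, and the documents do not say how far its effect is shared.
- **Only about five practitioners.** The figure in Protocol 3.4 is an expected number of interviews; Protocol 2.7 provides for additional staff.
- **NHS Digital recruits have no site.** Neither document says so. What can be said is that delivery is from one hub (Protocol 2.9.1) and some participants self-refer (Protocol 2.5), so site needs a definition.
- **The fallback also drops unequal variances.** This is inferred from the contrast between usual and heteroscedastic regression, and would matter little with arms this similar in size.

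**Conclusion.** The point holds at moderate priority. The primary model can change on an undefined, data-based judgement. The clustering unit is inconsistent between SAP 5.1.1, SAP 5.2 and Protocol 6.2.1, while the sample size rests on therapy group and SAP section 8 declares no deviation.

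The numerical effect is small. With group as the unit, type I error is about 5.0 to 5.2% at ICC 0.01 under an F-test trigger, about 5.4 to 5.7% at ICCs of 0.03 to 0.10, and 4.6 to 5.0% throughout under an estimated-ICC trigger of 0.01. These figures rest on assumed triggers, assumed ICCs above 0.01, equal group sizes and no covariates. The case for changing the text is prespecification, not a large error rate. The documents do not support a reading that the headline result is at an analyst's disposal or that anyone has seen results by arm.

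**What to change.** 1. Delete the fallback sentence in SAP 5.1.1.
2. Name one primary model: a linear mixed model with a random effect for therapy group in the intervention arm only (each control a singleton), arm-specific residual variances, and a small-sample degrees-of-freedom method such as Satterthwaite or Kenward-Roger. Keep it whatever the estimated variance.
3. Use the same structure for the unadjusted, secondary continuous and subgroup analyses.
4. Move practitioner, site and ordinary regression to named sensitivity analyses, and define site if it is kept there.
5. Record the departure from the protocol's site random effect in SAP section 8.

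The cost is SAP wording, including a declared departure from the protocol, and a confidence interval about 1 to 2% wider at ICC 0.01 than ordinary regression would give. No new sample size is needed, because 535 already includes the design effect of 1.07.
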